### *Secondary analyses*

The effect of warming strategy on collapsed composite of 30-day deep or organ-space surgical site infection and readmission within a month of surgery will be assessed using separate chi-square tests or multivariable logistic regression models, as appropriate.

The effect of warming strategy on the intraoperative transfusion requirement, defined as units of red blood cells transfused, will be assessed using a multivariable Poisson or negative binomial regression model, as appropriate.

Finally, the effect of warming strategy on time to discharge alive will be assessed using a Cox proportional hazards regression model. Patients who died before discharge will be assigned a censoring time equal to the longest observed duration of hospitalization.

To assess the robustness of our primary analysis, we will conduct per-protocol analysis for primary outcome by analyzing the subset of patients who completed the treatment originally allocated and without missing outcome data. This analysis is expected to be biased in favor of the preferred treatment and therefore no inference will be made about results.

### *Exploratory analyses*

Groups will be compared on estimated intraoperative blood loss; the change in blood hemoglobin from preoperatively until the first postoperative morning, adjusted for interim transfusions; and quality-of-recovery 15 on the third postoperative day. We will use multivariable linear regression models, adjusted for potential confounders. The effect of warming strategy on 30-day superficial surgical site infection and myocardial infarction will be assessed using a chi-square test or multivariable logistic regression model.

Moreover, the association between the time-weighted intraoperative core temperature and the primary outcome will be assessed using a multivariable logistics regression model, adjusted for all potential confounders.

We will use an overall alpha of 0.05 for each of the primary, secondary, and tertiary analyses. Specifically, the significance criterion is 0.05 for primary analysis, 0.0125 for each secondary analysis (i.e., 0.05/4, Bonferroni). Holm-Bonferroni correction will be used for the exploratory analysis.

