For patients with a chronic elevation or an acute myocardial injury before surgery, a new myocardial injury after surgery requires identification of a new elevated troponin after surgery as per points 1-5 above, and the troponin elevation must be a 20% rise beyond the chronic troponin value or beyond the last measurement of the acute preoperative myocardial injury that was clearly demonstrated to have peaked and was coming down. Patients meeting diagnostic criteria for MINS will be evaluated for myocardial infarction with EKG and ECHO with cardiac consultation, which will help us detect all infarctions and increase the baseline incidence.

**Secondary outcomes** will include:

- 1) 30-day deep or organ-space surgical site infection, as defined by Center for Disease Control criteria\*;
- 2) Intraoperative transfusion requirement, defined as units of red blood cells transfused;
- 3) Duration of hospitalization (censored at 30 days);
- 4) Readmission within a month of surgery;

Exploratory outcomes will be:

- 1) Estimated intraoperative blood loss;
- 2) The change in blood hemoglobin from preoperatively to the first postoperative morning;
- 3) 30-day superficial surgical site infection;
- 4) Quality-of-recovery 15 on the third postoperative day in person or by phone in patients already discharged;
- 5) 30-day myocardial infarction meeting requirements of the Third Universal Definition.

\*Definitions of surgical site infections, modified from 1990 CDC criteria: <http://www.cdc.gov/hicpac/SSI/table1-SSI.html>.

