### *Primary analysis*

We will assess the effect of warming strategy on the binary-event composite of myocardial injury, non-fatal cardiac arrest, and all-cause mortality within 30 days of surgery, using a multivariate generalized estimating equations (GEE) method. A common effect GEE test with an unstructured working correlation matrix will be performed, assuming that each component is similarly affected by intervention. The treatment-by-component interaction will be examined in a separate distinct effects GEE model to assess the heterogeneity of the treatment effect across outcomes.

Secondly, we will estimate the average relative effect of aggressive warming across the three categories of complications, using a GEE 'distinct effects' model with an unstructured working correlation matrix. This method is not driven by component with the highest frequency but may have a lower power compared to common effects model because one complication has a lower expected incidence. Regardless of the existence of the interaction, we will report the treatment effect of aggressive warming for each complication. The significance criterion will be 0.017 for each association (i.e., 0.05/3, Bonferroni).

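### Holm would control the secondary family at the same 0.05 as the planned fixed 0.0125 and would lose no rejections; the power gain is useful only if several secondary effects are real

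*Combined protocol and SAP*

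**What the plan says.** The significance criteria stand at the end of the Exploratory analyses section: "We will use an overall alpha of 0.05 for each of the primary, secondary, and tertiary analyses". The criterion for the secondary family, followed directly by a different method for the exploratory family, reads: "0.0125 for each secondary analysis (i.e., 0.05/4, Bonferroni). Holm-Bonferroni correction will be used for the exploratory analysis".

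The Measurements section lists four secondary outcomes:
- "30-day deep or organ-space surgical site infection, as defined by Center for Disease Control criteria"
- "Intraoperative transfusion requirement, defined as units of red blood cells transfused"
- "Duration of hospitalization (censored at 30 days")
- readmission within a month

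The Secondary analyses section tests infection and readmission separately, so the family has four tests and the divisor of 4 is right.

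The Primary analysis section makes the same single-step choice for the three components of the composite: "The significance criterion will be 0.017 for each association (i.e., 0.05/3, Bonferroni").

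No section says why the step-down method is kept for the exploratory family. None gives an assumed rate, effect size or power for any secondary outcome.

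**The concern.** Under a fixed threshold, each secondary P-value is compared with 0.0125 whatever the other three show. A P of 0.015 is declared negative even when another secondary outcome is clearly positive. Holm relaxes the threshold after each rejection and still holds the familywise error that the plan itself sets. The plan thus uses the more powerful procedure for its less important family.

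What is at stake is which secondary findings can be declared. The Background says that randomized trials of mild hypothermia showed effects on transfusion, surgical site infection and hospital stay. Those are three of the four secondary outcomes, and several real effects is the situation in which Holm helps. The Sample-size Estimate powers only the primary outcome, so power for the secondary outcomes may be modest.

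**Working it through.** **Inputs from the plan.** Family alpha 0.05; four tests; 0.0125 each; 2401 analysed patients per group (Sample-size Estimate).

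**The plan's figure.** 0.05/4 = 0.0125 reproduces exactly. If all four nulls are true and the tests are independent, familywise error is 1 − (1 − 0.0125)^4 = 0.049.

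**Holm thresholds.** Order the P-values from smallest to largest and compare them with 0.05/4 = 0.0125, 0.05/3 = 0.0167, 0.05/2 = 0.025 and 0.05/1 = 0.05. Stop at the first failure.

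**Example with invented P-values.** Take 0.004, 0.015, 0.020 and 0.040. At a fixed 0.0125 only the first is significant. Under Holm, 0.004 ≤ 0.0125, 0.015 ≤ 0.0167, 0.020 ≤ 0.025 and 0.040 ≤ 0.05, so all four are.

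**Simulation (assumptions, not in the documents).** Four independent two-sided z-tests. Each true effect has either 80% power at 0.0125 (mean z = 2.498 + 0.842 = 3.34) or 30% power (mean z = 2.498 − 0.524 = 1.97). In every replicate Holm rejected everything that Bonferroni rejected.

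At 80% power, Bonferroni then Holm:

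| True effects | Average power | All true effects declared | Familywise error |
|---|---|---|---|
| 0 | – | – | 0.049, 0.049 |
| 1 | 0.800, 0.801 | 0.800, 0.801 | 0.037, 0.047 |
| 2 | 0.80, 0.82 | 0.64, 0.69 | 0.025, 0.044 |
| 3 | 0.80, 0.85 | 0.51, 0.64 | 0.013, 0.041 |
| 4 | 0.80, 0.89 | 0.41, 0.69 | – |

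The Bonferroni entries agree with direct arithmetic: 0.8^4 = 0.41 for declaring all four effects, and 1 − 0.9875^2 = 0.025 for familywise error with two nulls left.

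With correlation 0.3 between tests, Holm's average power with two, three or four true effects is 0.82, 0.85 and 0.88. The chance of declaring all true effects rises from 0.67 to 0.71, 0.57 to 0.68 and 0.50 to 0.73.

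At 30% power the gains in average power are about 0.1, 1.3, 2.7 and 4.5 points for one to four true effects.

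**Where secondary power might lie (assumed rates).** With a 5% control rate, a 30% relative reduction and 2401 per group, power for a binary outcome is 53% at 0.0125, 57% at 0.0167, 63% at 0.025 and 73% at 0.05. Five assumed combinations were tried, with control rates of 2% to 8% and reductions of 20% to 30%. Across them, power ran from 19% to 59% at 0.0125 and from 36% to 78% at 0.05.

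**Component tests.** The Sample-size Estimate gives rates of 10% (myocardial injury), 0.1% (arrest) and 1% (death). With a 30% reduction in each, 2401 per group, independent tests and a normal approximation, moving from a fixed 0.0167 to Holm leaves power for myocardial injury at about 91%. Death moves from about 10% to 13%, and arrest from about 2% to 4%. The approximation is poor for arrest, where about 2401 × 0.001 = 2.4 events are expected in the control group.

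**The case against.** The strongest reply is that nothing here is wrong. The threshold is correctly derived, and a stricter, simpler rule for secondary outcomes is a legitimate choice. No primary result, sample size or estimate changes. That stands, and it limits the point to an inexpensive improvement.

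A reader might infer that Bonferroni buys no error control at all. That goes too far. Both methods have the same 0.05 bound and the same error when every null is true. When some effects are real, Bonferroni leaves error unspent and Holm uses it: 0.025 becomes 0.044 with two true effects and 0.013 becomes 0.041 with three. Holm stays within the plan's limit, but the increase should be acknowledged.

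A reader might also take all four effects as likely and quote the rise from 0.41 to 0.69. The documents do not support that. The Background names transfusion, infection and hospital stay, and reports no effect on readmission. Even for those three, the Human Subjects section says that warming recommendations rest on about 34.5°C against 36.5°C. It adds that the only study to show an effect of a 0.5°C difference found no significant difference in transfusion requirements, and that no outcome study has examined 37°C or above.

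The gain is also conditional. The smallest P-value faces 0.0125 under either method, so with four real effects the chance of at least one significant result is unchanged. With one real effect the gain is about 0.1 point.

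Finally, Bonferroni has simple matching 98.75% intervals. The plan neither specifies them nor gives them as its reason, but Holm would lose that option.

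**Conclusion.** The point holds as an avoidable inefficiency. For the familywise error that the plan targets, Holm gives the same guarantee under any dependence and never rejects less. That comparison needs no assumption about rates or correlation.

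The size of the gain does rest on assumptions. At 80% marginal power and independence, it is about 0.1, 2, 5 and 9 points of average power with one, two, three or four true effects. At 30% marginal power it is about 0.1 to 4.5 points. The documents contain nothing that would fix where this trial lies in that range.

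Extending the step-down to the three component tests would be consistent, but the check shows no material gain there. The components are not a reason for the change.

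**What to change.** Before unblinding, replace the fixed 0.0125 criterion in the Exploratory analyses section with wording such as: the four secondary outcomes will be tested with Holm's procedure at a family alpha of 0.05 (ordered thresholds 0.0125, 0.0167, 0.025 and 0.05), and Holm-adjusted P-values will be reported.

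State that any 95% confidence intervals for secondary outcomes are not adjusted for multiplicity. Without that label the two can appear to conflict. If the smallest P-value is 0.04, its unadjusted 95% interval excludes the null, while its Holm-adjusted P is 4 × 0.04 = 0.16.

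Applying the same step-down (0.0167, 0.025, 0.05) to the three components in the Primary analysis section is optional.

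The cost is one or two sentences, using a method the plan already names. Sample size, group sequential boundaries and the primary test are untouched. The timing matters because a switch made after results are known would look data-driven.

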### **Sample-size Estimate**

[figure not shown]
Amongst 10,000 patients enrolled in POISE-2, 8,449 met the inclusion criteria proposed for PROTECT. The incidence of MINS, nonfatal cardiac arrest, and total mortality within 30 days post-operatively were 10%, 0.1% and 1% respectively. These studies were largely conducted outside the United States and we can thus assume that most patients were either unwarmed or inadequately warmed. We will thus assume that patients assigned to routine management will have a similar incidence of our composite outcome.

A total of 4000 patients will give a power of 0.9 at the 0.05 significance level to detect a 30% or more relative reduction in the primary outcomes, comparing routine

thermal management group to aggressive warming group. Sample size was calculated for common effect GEE model with unstructured covariance matrix, assuming a correlation of 0.1 between outcomes. We estimated sample size using the MULTBINPOW SAS macro [Mascha EJ Power Calculation for Tests on a Vector of Binary Outcomes], which can estimate the power for multivariate GEE model given varying correlation and sample size.

After accounting for interim analysis at each 25% of the maximum enrollment (3 interim analyses and a final analysis, as needed), a maximum of 4802 patients would be needed (2401 per group) for the analysis.

For the primary analysis, we will use a group sequential design with a nonbinding beta boundary, employing a gamma spending function with parameter gamma of -4 for efficacy and 0 for futility, thus spending beta (for futility monitoring) considerably faster than alpha (for efficacy monitoring). Boundaries for efficacy (futility in parentheses) at the each interim and final analyses are  $P \leq 0.001$  ( $P > 0.880$ ),  $P \leq 0.005$  ( $P > 0.525$ ),  $P \leq 0.014$  ( $P > 0.169$ ), and  $P \leq 0.044$  ( $P > 0.044$ ), respectively, based on an anticipated 30% treatment effect. Figure 1 shows the z-statistic boundaries for efficacy and futility at each interim look.

**Figure 1. Group sequential boundaries** for efficacy (bottom, dark blue), harm (top, dark blue) and futility (light blue) assuming 4 possible looks (3 interim and final). Y-axis is the standardized treatment effect (difference in proportions / standard error of difference). X-axis depicts cumulative proportion of total sample size over time. The standardized Z values corresponding to the boundaries are presented in the table below. A sample size of 4802 in total is needed, assuming 4000 in fixed sample design, 90% power and alpha=0.05. SAS version 9.4 or higher (SAS Institute, Cary, NC, USA) and R software version 3.2.1 or higher (R Project for Statistical Computing, Vienna, Austria) will be used for the analyses.

Table 1 provides the probabilities of stopping the trial for the underlying true treatment effect. Alternative (30% risk reduction), half-way between Null and Alternative and 1.5 times the alternative effect. For example, if the alternative hypothesis were true, the cumulative probability of crossing either efficacy or futility boundary at the 1st, 2nd, 3rd and 4th looks would be 0.109, 0.437, 0.812 and 1 respectively.

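### The printed efficacy P thresholds at looks 1 and 3 (0.001 and 0.014) do not match the stated gamma(-4) spending function (0.0016 and 0.0147) or Table 1; the discrepancy is conservative and minor

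*Combined protocol and SAP*

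**What the plan says.** All of this is in the Sample-size Estimate section of the combined protocol and SAP, with Figure 1 and Table 1.

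- **Looks:** "interim analysis at each 25% of the maximum enrollment (3 interim analyses and a final analysis, as needed".
- **Spending rule:** a group sequential design with nonbinding futility, "employing a gamma spending function with parameter gamma of -4 for efficacy and 0 for futility".
- **Thresholds:** "Boundaries for efficacy (futility in parentheses) at the each interim and final analyses are", followed by efficacy P values of 0.001, 0.005, 0.014 and 0.044.
- **Sidedness:** the Figure 1 caption describes boundaries "for efficacy (bottom, dark blue), harm (top, dark blue) and futility (light blue) assuming 4 possible looks (3 interim and final"), so the design is two-sided.
- **Size:** "A sample size of 4802 in total is needed, assuming 4000 in fixed sample design, 90% power and alpha=0.05".
- **Operating characteristics:** under the alternative, the cumulative probabilities of stopping "would be 0.109, 0.437, 0.812 and 1 respectively". Table 1 repeats these and adds three rows. Its stage-1 entries are 0.121 (null), 0.093 (half-way), 0.109 (alternative) and 0.315 (1.5 times the alternative).

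The Figure 1 caption also says that a table of z values accompanies the figure. Neither the figure nor that table is in the text available for review.

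**The concern.** Once alpha, the spending function and the look times are fixed, the efficacy boundaries are fixed too. The section states all three and then prints a list that does not follow from them at looks 1 and 3. No single convention produces the list. Rounding the exact values to three decimals gives 0.002, 0.005, 0.015 and 0.044; truncating gives 0.001, 0.004, 0.014 and 0.044. The printed list takes the truncated value at looks 1 and 3 and the rounded value at look 2. That the two values were cut off is an inference; the document does not explain them.

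What is at stake is whether the stopping rule has one reading. A first-look P of 0.0013, for example, crosses the boundary under the stated function and does not cross it under the printed number.

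**Working it through.** **Inputs (all from the Sample-size Estimate section and Figure 1 caption).** Two-sided alpha 0.05; power 0.90; fixed-design N 4000; looks at t = 0.25, 0.50, 0.75 and 1.00; gamma -4 for alpha and 0 for beta; nonbinding futility. The fixed N of 4000 is taken as given, since it comes from a GEE power macro; the efficacy boundaries do not depend on it.

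**1. Alpha spent.** The formula is α(t) = 0.05 × (1 − e^{4t}) / (1 − e^{4}).

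At look 1 no integration is needed, because the nominal P equals the alpha spent: 0.05 × (e − 1)/(e⁴ − 1) = 0.05 × 1.7183/53.598 = 0.00160.

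Cumulative spending at the four looks is 0.0016, 0.0060, 0.0178 and 0.0500.

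**2. Boundaries.** Solving recursively by numerical integration, ignoring futility because it is nonbinding:

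| Look | z | Exact two-sided P | Printed P |
|---|---|---|---|
| 1 | 3.155 | 0.0016 | 0.001 |
| 2 | 2.818 | 0.0048 | 0.005 |
| 3 | 2.439 | 0.0147 | 0.014 |
| 4 | 2.014 | 0.0440 | 0.044 |

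**3. Reproduce the plan's own figures.** With beta spending 0.10t and an inner futility region, the drift at which the efficacy and futility boundaries meet at the final look is 3.5514. Then N = 4000 × (3.5514/(1.9600 + 1.2816))² = 4801.3, against 4802 stated.

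Cumulative stopping from the exact boundaries:

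| Row | Recomputed, stages 1–3 | Table 1 |
|---|---|---|
| Null | 0.1211 / 0.5258 / 0.8718 | 0.121 / 0.526 / 0.872 |
| Half-way | 0.0925 / 0.3451 / 0.6752 | 0.093 / 0.345 / 0.675 |
| Alternative | 0.1088 / 0.4369 / 0.8117 | 0.109 / 0.437 / 0.812 |
| 1.5 × alternative | 0.3150 / 0.8361 / 0.9875 | 0.315 / 0.836 / 0.988 |

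The design calculation is therefore sound, and Table 1 matches the exact boundaries.

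**4. Repeat stage 1 with the printed threshold.** P = 0.001 corresponds to z = 3.291. Under the alternative the look-1 mean is 3.5514 × √0.25 = 1.776.

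- Efficacy crossing, exact boundary: 1 − Φ(3.155 − 1.776) = 0.084.
- Efficacy crossing, printed threshold: 1 − Φ(3.291 − 1.776) = 0.065.
- Futility (inner region, z = 0.150) adds 0.025 in both cases.
- Total: 0.109 exact, 0.090 printed.

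At 1.5 times the alternative the mean is 2.664. The efficacy crossing is 0.311 exact against 0.265 printed, and the totals are 0.315 and 0.269.

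The half-way row differs slightly (0.089 printed threshold, 0.093 in Table 1). The null row does not discriminate (0.121 either way). At stage 3 the alternative row gives 0.806 with the printed values, against 0.812 in Table 1.

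**5. Overall error rates.** Cumulative two-sided alpha with the printed efficacy list is 0.0010, 0.0057, 0.0168 and 0.0494. This lies below the spending function at every look. Power at N = 4802 is 0.8997, against 0.900.

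**6. Alternative readings tried.** Each was tested to see whether it yields the printed list.

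- One-sided 0.025 gives the same two-sided P values.
- One-sided 0.05 gives 0.0016, 0.0049, 0.0151 and 0.0452.
- Binding futility gives 0.0016, 0.0048, 0.0151 and 0.0555, with N about 4564.
- A gamma between about -4.1 and -4.2 could round to the printed set, but it contradicts the stated -4 and would put the alternative's stage-1 entry at about 0.103 to 0.106.

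**The case against.** The strongest reply is that the printed P values only report the rule. The rule is the spending function, and the Figure 1 caption says z values are tabulated. If that unseen table holds 3.155, 2.818, 2.439 and 2.014, the plan already contains the correct boundaries. This stands in part. The absence of the table from the available text is not a fault of the plan, and the correction is then only to align the P list with it. But the P list would still disagree with the spending function and with Table 1.

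It is also fair to say that nothing shows the DSMB would act on the three-decimal list. The Trial Management section does not say which form of the boundary it uses, and the P list names efficacy and futility only; harm appears in the Figure 1 caption. A reader might infer that the board would have applied a wrong threshold. The documents do not support that.

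The direction of the error and its small cost in power also count against any serious consequence. So does the amendment log entry of 10/29/2020, which records the decision to skip the third interim and so leaves the look-3 discrepancy with little practical weight.

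**Conclusion.** The printed efficacy thresholds at looks 1 and 3 are wrong for the stated design. Look 1 carries the point: 0.001 is about 38% below the designed 0.0016 (1 − 0.0010/0.0016), and using it lowers the chance of a first-look efficacy crossing from 0.084 to 0.065 under the alternative. At look 3 the gap in P is 0.0007.

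The severity is minor. A reader might infer that type I error is compromised or that the sample size is wrong; neither follows. Overall alpha would be 0.0494, power is 0.90 to two decimals, and 4802 and Table 1 reproduce from the exact boundaries. The contradiction with Table 1 at stage 1 is clear in the alternative and 1.5-times rows, slight in the half-way row, and of no consequence in the null row.

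The conclusion assumes a two-sided 0.05 design with four equally spaced looks, as the section and the Figure 1 caption describe.

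**What to change.** Print the efficacy P values in the Sample-size Estimate section to four decimals: 0.0016, 0.0048, 0.0147 and 0.0440. Check that they agree with the z-value table mentioned in the Figure 1 caption (z about 3.155, 2.818, 2.439 and 2.014). Add a statement that the z values from the gamma(-4) spending function govern if any rounded figure differs. These values are for the four-look schedule as written.

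The cost is one corrected sentence and one added sentence. The sample size, Table 1 and the spending functions stay as they are.
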